7.3.5. Phase 1 Individual Patient Stopping Rules

The following safety events will trigger individual patient treatment discontinuation:

- Any DLT observed during Phase 1, within 28 days after starting treatment with TP-0184 as described in [Section 7.4](#)
- Any related AEs that lead to treatment discontinuation per [Section 7.4](#)
- Evidence of disease progression based on IWG Response Criteria for MDS 2006

7.4. Dose Adjustment Criteria

Dose adjustments may be permitted for patients who experience toxicities. These toxicities will be discussed by the Investigators and Medical Monitor to determine if it would be in the best interest of the patient to continue to receive a reduced dose of TP-0184. Dose adjustments due to study drug related non-hematologic or hematologic AE severity are described in [Table 4](#) and [Table 5](#), respectively.

Decisions to reinstate dosing following a toxicity for which drug was held will be determined by the Investigator and Medical Monitor. In patients who receive subsequent and/or multiple treatment cycles, the TP-0184 dose may be reduced by one dose level based on the observed AE that occurred during the preceding cycle.

If further significant AEs occur during one or more cycles at the new reduced dose level, an additional dose reduction may occur (this allows for two dose reductions) EXCEPT in the first dose cohort where only one dose reduction (-1) will be permitted. If non-hematologic AE(s) > Grade 3 occur at the -1 dose the patient may be discontinued from the study pending discussion with the Investigator and Medical Monitor.

In the Phase 1 portion of the study, no dose re-escalations will be allowed for any patient who had a previous dose reduction due to AEs.

The Phase 2 treatment dosing schedule will be determined by the SRC and SDP Oncology clinical team based on the recommended Phase 2 treatment dose, and the MTD or MAD from Phase 1 safety data.

Guidelines for dose adjustments of TP-0184 following Cycle 1 and resolution of a patient's non-hematologic AE(s) to \leq Grade 1 and/or hematologic AE(s) to baseline CTCAE Grade are provided in [Table 4](#) and [Table 5](#), respectively.

Table 4 Guide to TP-0184 Dose Adjustments Due to TP-0184 Related Non-Hematologic AE

Non-hematological AE Grade	Action Regarding TP-0184 Dosage
Grade 1 – non-hematologic	None - maintain current dose level
Grade 2 – non-hematologic	Results in dose delay until AE severity recovers to \leq Grade 1. The investigator has the option to reduce dose by 1 dose level within the current or at the next cycle (beyond cycle one) with agreement of the Medical Monitor
Grade 3 ^a – non-hematologic ^b	Hold, then reduce dose by 1 dose level upon recovery to \leq Grade 1 with agreement of the Medical Monitor.
Grade 4 – non-hematologic	Discontinue treatment.

^a Excluding brief (based on the investigator's judgment) Grade 3 vomiting or diarrhea, electrolyte abnormalities lasting less than 72 hours with optimal management.

^bIf an AE meets definition of DLT, discontinue treatment.

Table 5 Guide to TP-0184 Dose Adjustments Due to TP-0184 Related Hematologic AE

Hematologic AE Grade	Action Regarding TP-0184 Dosage
Grade 1 – hematologic	None - maintain current dose level
Grade 2 – hematologic	None - maintain current dose level
Any hematologic AE \geq Grade 3 (except anemia or platelets and ANC decrease)	Dose delay until resolved to \leq Grade 1 or baseline and then reduced by one dose level
Grade 4 platelets or ANC decrease	Dose delay if recovery to \leq Grade 3 within 7 days then reduce by one dose level. Discontinue if no recovery within 7 days.
Increase of Hgb \geq 2.0 g/dL over a duration of 2 weeks	Reduce dose by one dose level, if Δ Hgb not influenced by RBC transfusions and in the absence of volume depletion (dehydration)
Hgb \geq 11.5 g/dL, in the absence of RBC transfusion or volume depletion (dehydration)	Dose delay ^a until Hgb \leq 11.0 g/dL

^a Hemoglobin should be checked on a weekly basis.

Patients who are not able to be treated after a 6-week dose delay due to drug-related toxicity will, in general, be discontinued from treatment. However, for patients who have shown a beneficial response to TP-0184, consideration of treatment continuation will be discussed by the Investigator and Medical Monitor.

7.4.1. Management of Nonhematologic and Hematologic Toxicities

Nonhematologic and hematologic AEs may be treated with concomitant medications which are not prohibited in this study (Section 9.2.1), as deemed clinically indicated by the Investigator. All transfusion treatments for anemia and thrombocytopenia, and concomitant medications, must be recorded in the source and on the appropriate case report form (eCRF).

Antiemetics (ie, 5 hydroxytryptamine [5-HT3] receptor inhibitor or other antiemetic medications) are permitted according to standard practices at each investigational site.

Prophylactic antibiotic, antiviral, and/or antifungal therapy is allowed at the discretion of the Investigator and according to institutional standards.

Support with growth factors (eg, filgrastim) is not allowed except in the situation of life-threatening infections (eg, a Grade 4 sepsis with life-threatening infection with ongoing neutropenia). Whether the patient can continue TP-0184 dosing following treatment with growth factor support will be considered following discussion with the Medical Monitor.

Both onset of new hematologic and non-hematologic adverse events that are \geq Grade 4 and considered related to study drug treatments should be discussed with the Medical Monitor to determine whether a dose reduction ([Table 4](#) and [Table 5](#)) or treatment discontinuation should occur.

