8.3.1. Reasons for Treatment Discontinuation

A patient may be discontinued from TP-0184 treatment for any of the following reasons:

- In Phase 1, patient experiences a DLT during Cycle 1
- Failure to achieve a hematologic response. Patients not demonstrating evidence of hematologic response after the first 6 cycles (24 weeks) of treatment will be considered for treatment discontinuation, although with permission of the Medical Monitor and Investigator, TP-0184 study treatment may continue if clinically indicated and provided there is no evidence of Grade 4 toxicity.
- Grade 4 toxicity not responding to supportive measures and without a response to treatment
- The occurrence of any other AE, concurrent illness or laboratory abnormality which, in the opinion of the Investigator, warrants treatment discontinuation
- Patient noncompliance, defined as refusal or inability to adhere to the study schedule
- At the request of the patient, Investigator, SDP Oncology, or regulatory authority
- Patient is lost to follow-up
- Patient becomes pregnant while on study
- Patient begins another treatment for their disease
- Patient death
- Patient withdrawal of consent.

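### For a drug-related Grade 4 non-hematologic adverse event outside the Phase 1 Cycle 1 DLT rule, Table 4 requires stopping, while Section 7.4.1 and the -1-dose sentence in Section 7.4 leave it to discussion, and no text takes precedence

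*Protocol*

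**What the plan says.** Four places in the protocol bear directly on the event, and a fifth refers to them.

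- **Section 7.4, Table 4, Grade 4 row.** The action is "Discontinue treatment". The row has no hold, reduction or discussion option. The tables cover events related to TP-0184 and are introduced with the words "Guidelines for dose adjustments of TP-0184 following Cycle 1 and resolution of a patient's non-hematologic AE(s) to" Grade 1 or lower.
- **Section 7.4, text before Table 4.** If non-hematologic events above Grade 3 "occur at the -1 dose the patient may be discontinued from the study pending discussion with the Investigator and Medical Monitor".
- **Section 7.4.1, last paragraph.** It begins "Both onset of new hematologic and non-hematologic adverse events that are" Grade 4 or higher, and says that those "considered related to study drug treatments should be discussed with the Medical Monitor to determine whether a dose reduction" or treatment discontinuation should occur. Tables 4 and 5 are cited next to the words on dose reduction.
- **Section 8.3.1.** The list opens "A patient may be discontinued from TP-0184 treatment for any of the following reasons". One reason is "Grade 4 toxicity not responding to supportive measures and without a response to treatment". Another is "The occurrence of any other AE, concurrent illness or laboratory abnormality which, in the opinion of the Investigator, warrants treatment discontinuation".
- **Section 7.3.5 (Phase 1 individual stopping rules).** Treatment ends for any DLT within 28 days of starting, and for related events that lead to discontinuation under Section 7.4.

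**The concern.** A Grade 4 event is life-threatening by the protocol's own severity scale (Section 12.1.6.2.3), so a site needs one instruction. A site that opens Table 4 ends treatment. A site that opens Section 7.4.1 calls the Medical Monitor and may continue at a lower dose. Both would be following the protocol.

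Two things are at stake. The first is patient safety: whether treatment continues could depend on which page was read. The second is a reported result. Dose interruptions and dose reductions are named in the Phase 1 primary endpoint and in the Phase 2 secondary safety endpoint (Sections 6.1 and 6.2). The same clinical event could be counted as a dose reduction at one site and not at another.

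**Working it through.** The point involves no sample size, error rate or event count, so there is nothing to compute. The check is to follow one event, a related Grade 4 non-hematologic adverse event, through each setting.

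| Setting | Table 4 | Section 7.4.1 | Other text |
|---|---|---|---|
| Phase 1, Cycle 1 | Stop | Discuss: reduce or stop | DLT: Sections 7.3.5 and 7.4.2 require discontinuation |
| Phase 1, after Cycle 1, above the -1 dose | Stop | Discuss: reduce or stop | Section 7.3.5 defers to Section 7.4 |
| Patient at the -1 dose, after Cycle 1 | Stop | Discuss: reduce or stop | Section 7.4 text: *may* be discontinued, pending discussion |
| Phase 2 | Stop | Discuss: reduce or stop | No DLT rule |

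1. **Phase 1 Cycle 1.** Section 7.4.2 counts non-hematologic toxicity of Grade 3 or higher as a DLT. Its listed exceptions are read here as Grade 3 exceptions, so a Grade 4 event is a DLT and the patient is discontinued. Section 7.4.1 has no Cycle 1 carve-out, but the DLT text is explicit. This setting is treated as settled.

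2. **Does the cross-reference in Section 7.4.1 resolve the rest?** For hematologic events it does. Table 5 gives, for Grade 4 platelet or neutrophil decreases, a delay followed by reduction by one level if there is recovery within 7 days, and discontinuation otherwise. Both outcomes named in Section 7.4.1 therefore exist in Table 5. For non-hematologic events it does not. Table 4 offers reduction at Grades 2 and 3, with the Medical Monitor's agreement, and neither at Grade 4. Section 7.4.1 nevertheless names non-hematologic events expressly. If Table 4 governed, the discussion would have nothing to decide.

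3. **The -1-dose sentence.** This lies within the same section as Table 4 but is permissive where the table is unconditional. Table 3 lists no level below -1, so the reduction contemplated in Section 7.4.1 has no planned level to go to. The sentence also speaks of discontinuation from the study, whereas Table 4 speaks of treatment.

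4. **The Phase 1 stopping rule.** Section 7.3.5 applies when Section 7.4 leads to discontinuation. Whether it does so is the open question, so the rule cannot settle it.

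5. **Section 8.3.1.** Its Grade 4 bullet has two joint conditions: no response to supportive measures, and no response to treatment. It is also not limited to related or to non-hematologic events. On the point at issue it is worded more narrowly than Table 4, which has neither condition.

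6. **Precedence.** None of these sections says which text prevails.

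**The case against.** The best case for the plan has four parts.

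- **The texts can be read together.** Section 7.4.1 covers both kinds of event and cites both tables, so reduction might be meant for Table 5 events and discontinuation for Table 4 events. Both tables are titled as guides, and Section 7.4 opens by saying that toxicities will be discussed with the Medical Monitor. This softens the conflict but does not remove it. The sentence asks for a case-by-case determination for non-hematologic events too, and a guide that Section 7.3.5 uses as a stopping trigger needs a stated status.
- **The Medical Monitor limits variation between sites.** That is true for sites that follow Section 7.4.1. A site that follows Table 4 may stop without any such discussion.
- **Section 8.3.1 is not a rival rule.** A reader might infer that it lets a responding patient continue, making three conflicting stopping rules. The documents do not support that. The section lists permissible reasons to stop, includes a general reason resting on the Investigator's opinion, and does not say when treatment may continue. A site that discontinues under Table 4 does not breach it. This objection stands in full.
- **Discontinuation is not an endpoint.** A reader might infer that discontinuation counts are endpoints alongside dose reductions. They are not listed as such. Section 13.1.9.2.2 provides only for tabulating reasons for discontinuation and listing events that led to it. This also stands.

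**Conclusion.** The inconsistency is real and narrow. It lies between the Grade 4 row of Table 4 on one side and Section 7.4.1 and the -1-dose sentence of Section 7.4 on the other, for related non-hematologic events. It applies to Phase 1 after Cycle 1 and to Phase 2. Section 7.3.5 inherits it. Section 8.3.1 needs alignment but is not a further conflicting rule.

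On size, the plan foresaw approximately 30 patients in Phase 1 and up to 60 in Phase 2 (30 + 60 = 90), but the documents give no expected number of Grade 4 non-hematologic events. It would also be wrong to infer that trial results were distorted. SAP Section 2 reports that the study was terminated with two patients enrolled, dosed and discontinued, and that both will be shown in by-patient listings only. The realised impact is therefore small. The point matters mainly as a defect in the protocol text and for any later protocol that reuses it.

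The conclusion rests on two readings: that the Section 7.4.2 exceptions apply to Grade 3 only, and that Section 7.4.1 means what it says in including non-hematologic events. It is an internal inconsistency, not a question of design.

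**What to change.** Reconcile Table 4 (Grade 4 row), the -1-dose sentence in Section 7.4 and the last paragraph of Section 7.4.1 into a single rule for related Grade 4 non-hematologic events. Then:

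- correct the table citations in Section 7.4.1 so that each outcome it names exists in the table it cites;
- state whether the rule covers Phase 2 Cycle 1, given that the tables are introduced as applying after Cycle 1;
- use one term for stopping treatment as distinct from leaving the study;
- have Section 7.3.5 point to the reconciled rule, and align the Grade 4 bullet of Section 8.3.1 to it.

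Which action the rule should specify is a clinical decision for the sponsor, and no view is given here. The cost is protocol wording only: no added patients, visits or analyses.

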7.4.2. Dose-Limiting Toxicities

A DLT is defined as any one of the following events or abnormal laboratory value not clearly unrelated to the study drug observed within 28 days of starting treatment with TP-0184:

- Any death not clearly due to the underlying progression of disease (such as leukemic transformation)
- Any \geq Grade 3 non hematological toxicity except for Grade 3 of nausea, vomiting, diarrhea or clinically not significant lab abnormalities lasting 72 hours or less with adequate supportive care
- New onset cardiac failure or worsening symptomatic cardiac failure based on NYHA Functional Classification ([Appendix 11](#))
- ECHO or MUGA reduction of ejection fraction \geq 10%
- Any Grade 4 neutropenia (absolute neutrophil count (ANC) not recovering to $> 500/\mu\text{L}$ within 7 days in the absence of myelodysplasia or transformation to acute leukemia)
 - To determine progression of MDS / transformation to AML, a bone marrow biopsy / aspiration and/or peripheral blood can be performed
- Any Grade 3 thrombocytopenia associated with clinically significant bleeding or Grade 4 thrombocytopenia in the absence of myelodysplasia related marrow failure or transformation to acute leukemia
 - To determine progression of MDS / transformation to AML, a bone marrow biopsy / aspiration and/or peripheral blood can be performed
- All other hematological toxicity \geq Grade 3 other than defined above for ANC and platelets

Note: As Grade \leq 3 neutropenic and Grade 2 thrombocytopenic patients are included in the study, any new onset of Grade 4 neutropenia ($< 500/\mu\text{L}$ neutrophils) in a patient with prior history of chronic neutropenia with infection or Grade 3 decrease in platelets ($< 50\text{K}$ platelets) in patients with prior history of MDS-related thrombocytopenia with bleeding, will be evaluated by the SRC members and Medical Monitor in consideration as to whether a DLT has occurred. If determined that the Grade 3 or 4 hematologic AE is related only to the biology of MDS, no DLT will be declared.

Patients who experience a DLT during Cycle 1 will be discontinued from the study.

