8. SELECTION AND WITHDRAWAL OF PATIENTS

8.1. Inclusion Criteria

Each patient must meet the following criteria to be enrolled in this study:

1. A documented diagnosis of lower risk MDS (IPSS-R Low, Intermediate) according to WHO 2016 classification, de novo or secondary.
2. Bone marrow biopsy and/or aspirate performed pre-dose to assess disease status and available for review *prior* to full screening review. If the bone marrow biopsy and/or aspirate is nonproductive or nondiagnostic, the procedure must be repeated. Bone marrow biopsy/aspirate performed \leq 12 weeks prior to baseline will not need to be repeated if results and a minimum of 6 slides are available.
3. Relapsed, refractory/resistant, intolerant, or inadequate response to ESA treatment, as defined by the following:
 - Relapse according to IWG 2006
 - Refractory/resistant – documented non-response or response that is no longer maintained to prior ESA-containing regimen, either as single agent or combination (eg, with G-CSF). ESA regimen must have been either:
 - Recombinant human erythropoietin (rHu EPO) \geq 500 IU/wk for at least 8 doses or equivalent

OR

 - Darbepoetin alpha \geq 300 μ g Q3W for at least 4 doses or equivalent
 - Intolerant – documented discontinuation of prior ESA containing regimen, either as single agent or combination (eg, with G-CSF), at any time after introduction due to intolerance or an adverse event.
 - Inadequate response – in the absence of transfusions support, patients under ESA treatment for at least 12 weeks that do not show a rise in hemoglobin of greater than equal to 1 g/dl.
4. Patients with 5q deletions are allowed only if they have failed or are intolerant to lenalidomide treatment.
 - Failure or intolerance to lenalidomide defined as clinical and cytogenetic responses to according to the international working group 2006 MDS: (1) absence of response; (2) bone marrow progression during treatment with or without prior response; (3) secondary failure (loss of prior hematological response without bone marrow progression); or, (4) intolerance (treatment discontinuation due to AEs, with or without prior response) based on investigator judgement ([Prebet 2017](#)).
5. Previous treatment for anemia with or without RBC transfusion support:
 - a. Low transfusion burden (LTb), defined as requiring less than 4 red blood cell units in the 8 weeks before treatment (and baseline hemoglobin $<$ 9.0 g/dL)

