14. Platelet count $< 50,000/\mu\text{L}$ ($50 \times 10^9/\text{L}$) during screening.
15. Absolute neutrophil count (ANC) $< 500 / \mu\text{L}$ ($0.5 \times 10^9/\text{L}$) during screening.
16. Women who are pregnant or breastfeeding.

17. Male patients with partners of childbearing potential who are unwilling to use condoms in combination with a second effective method of contraception during the trial and for 7 months after the last administration of study treatment.
18. Inability to undergo MRI imaging.
19. Parenchymal iron overload by screening MRI.
20. Unwillingness or inability to comply with procedures required in this protocol.
21. Have undergone recent surgery with potential to cause the impairment of gastrointestinal tract absorption or that could cause short bowel syndrome with diarrhea due to malabsorption.
22. Have known hemochromatosis at baseline or a family history of hemochromatosis.
23. Presence of any psychological, familial, sociological or geographical condition that, in the opinion of the investigator, could potentially hinder compliance with the study protocol and follow-up schedule.
24. Any significant medical condition, laboratory abnormality, or psychiatric illness that would prevent the subject from participating in the study.
25. Live vaccines within 14 days prior to first study drug administration. COVID-19 vaccines (non-live) approved by regional health authorities are allowed.
26. Medications that are known strong to moderate CYP3A4 inducers must be discontinued at least 21 days prior to first dose of study drug. Medications that are known strong to moderate CYP3A4 inhibitors must be stopped 21 days (or 5 half-lives, whichever is shorter) prior to the first dose of study drug.
27. Patients who have received medications with known or possible risk of prolonging the QT interval or inducing Torsades de Pointes within the previous 7 days.

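### Read literally, the Grade 4 neutropenia DLT criterion can never be met in an MDS trial, so isolated prolonged neutropenia is not a DLT as printed

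*Protocol*

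**What the plan says.** All of the DLT wording is in Protocol section 7.4.2. The section's lead-in counts listed events within 28 days of starting treatment unless they are clearly unrelated to study drug.

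- **Neutropenia bullet.** Grade 4 neutropenia counts when the ANC does not recover above 500/µL "within 7 days in the absence of myelodysplasia or transformation to acute leukemia".
- **Its sub-bullet.** Marrow or blood testing may be done "To determine progression of MDS / transformation to AML".
- **Platelet bullet.** The parallel condition is causal: "Grade 4 thrombocytopenia in the absence of myelodysplasia related marrow failure or transformation to acute leukemia".
- **Catch-all hematologic bullet.** It covers Grade 3 or higher toxicity "other than defined above for ANC and platelets".
- **Note.** New Grade 4 neutropenia goes to the SRC and Medical Monitor when it arises "in a patient with prior history of chronic neutropenia with infection". If the event "is related only to the biology of MDS, no DLT will be declared".

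Elsewhere in the protocol:

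- Inclusion criterion 1 (section 8.1) requires "A documented diagnosis of lower risk MDS (IPSS-R Low, Intermediate" risk disease in every patient.
- Exclusion criterion 15 (section 8.2) bars an ANC below 500/µL at screening.
- Table 5 (section 7.4) delays dosing for related Grade 4 ANC decrease and stops treatment if there is no recovery in 7 days.
- Section 13.1.5 admits a patient without a DLT to the DLT analysis set only if the 28-day period is completed with at least 80% of planned doses. Other patients may be replaced.
- Section 7.3.3 gives the SRC the task of determining DLTs.

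**The concern.** A DLT criterion has to be capable of being true or false in the patients enrolled. Every patient here has myelodysplasia, so a condition requiring its absence always fails and the neutropenia bullet cannot fire. The other bullets do not close the gap for an isolated event.

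The DLT count is what the dose-escalation model uses. An event left out makes the dose look safer than the data show, and the model may then admit a higher dose that it would have barred.

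**Working it through.** **1. Does any route in 7.4.2 count the event?** Take Grade 4 neutropenia with no recovery in 7 days, no infection, and no history of chronic neutropenia with infection.

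| Route | Result as printed |
|---|---|
| Neutropenia bullet | Requires absence of myelodysplasia; never true |
| Catch-all hematologic bullet | ANC is excluded |
| Non-hematologic Grade 3+ bullet | Needs an infection or other non-hematologic event |
| Note | Does not reach this patient |
| Table 5 | Governs dosing; does not define a DLT |

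No route counts it. Because of exclusion 15, the event is also a fall from the screening value. A patient just above 500/µL could still dip from stable MDS, so some MDS exception is needed.

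**2. What happens to the uncounted patient?** There are two possibilities.

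- The patient is kept as a non-DLT, so the cohort reads 0/3.
- The patient becomes non-evaluable. The rule needs 0.80 × 28 = 22.4, so 23 doses. A 7-day hold inside Cycle 1 leaves at most 28 − 7 = 21 doses, or 75%. The cohort then reads 0/2 unless a replacement is added. This assumes that held doses count as planned and that the hold falls in Cycle 1; section 7.4 describes the adjustment guidelines as following Cycle 1.

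**3. Effect on the model.** Inputs from Appendix 2:

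- logit π(d) = log α + β log(d/90);
- bivariate normal prior on (log α, log β) with means (−0.847, 0.913), SDs (1.275, 0.482) and correlation −0.9 (Table 11).

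The model dose is the one with the largest P(0.16 < π ≤ 0.33) among doses with P(π > 0.33) < 0.25. The posterior was computed on a 1601 × 1601 grid over planned doses of 10 to 270 mg.

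*Check against the protocol.*

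- Table 12, prior P(over): 0.243 against the printed 0.2448 at 60 mg, and 0.456 against 0.4578 at 90 mg.
- Table 15, next dose: this matches in scenario 1 (P(over) 0.145 against 0.1462), scenario 3 (0.148 against 0.1501) and scenario 4 (0.148 against 0.1293).
- Scenario 2 does not reproduce. The grid gives P(over) 0.262 at 90 mg and so selects 60 mg; the table prints 90 mg with 0.2312.

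*Illustration.* The cohort has three patients, with 0/3 at every lower planned dose.

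| Cohort | Model dose, counted (1/3) | Omitted, 0/3 | Omitted, 0/2 | P(over) at the dose shown: 1/3, 0/3, 0/2 |
|---|---|---|---|---|
| 20 mg | 20 | 60 | 60 | 40 mg: 0.508, 0.054, 0.071 |
| 40 mg | 40 | 60 | 60 | 60 mg: 0.384, 0.061, 0.081 |
| 60 mg | 60 | 90 | 90 | 90 mg: 0.502, 0.148, 0.179 |
| 90 mg | 90 | 90 | 90 | 120 mg: 0.688, 0.393, 0.439 |
| 120 mg | 90 | 120 | 90 | 120 mg: 0.403, 0.215, 0.265 |
| 160, 210, 270 mg | 120 | 120 | 120 | not shown |

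In the first three cohorts, omission turns the next planned level from inadmissible to admissible under either handling. At 120 mg the result depends on the handling: 0.215 passes the 0.25 limit and 0.265 does not.

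The 270 mg result is close. With 0/3, P(over) at 160 mg is 0.259, just above the limit. If the printed scenario 2 value were used, the 40 mg cohort contrast under 0/3 would be 40 against 90 mg.

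**The case against.** The strongest reply is that the intent is already on the page. The sub-bullet names progression and transformation, the lead-in counts anything not clearly unrelated to drug, and the Note withholds a DLT only for an event due to MDS alone. A reading under which the bullet can never fire makes the bullet and its sub-bullet pointless. The SRC determines DLTs and reviews all safety data from each cohort. New related Grade 4 events go to the Medical Monitor (section 7.4.1), and section 7.3.1, Phase 1 Dose Escalation, treats model output as guidance. The toxicology and clinical summaries in section 5.4 report no neutropenia signal.

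Most of this stands as mitigation, and a sensible SRC would probably count the event. It does not cure the text. The sub-bullet says only that a test may be done, and the Note's review is tied to one subgroup, which invites the inference that other patients follow the bullet as printed.

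Three stronger readings are tempting and are not supported:

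- *That neutropenia can never lead to a DLT.* A Grade 3 or higher infection would count under the non-hematologic bullet, and patients in the Note's subgroup go to the SRC.
- *That omission raises the model dose at most levels.* It does so at 4 of 8 planned levels with 0/3, and at 3 of 8 with 0/2.
- *That an event was in fact missed.* The SAP (section 2) reports termination after two patients and plans listings only. Nothing in either document shows such an event.

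**Conclusion.** The criterion is wrong as written. Followed literally, it never counts isolated Grade 4 neutropenia that fails to recover within 7 days in a patient without prior chronic neutropenia with infection. That conclusion rests on the text alone.

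The size is illustrative. It assumes one omitted event, three-patient cohorts and no DLT at lower doses. The effect is concentrated at the three lowest levels, is conditional at 120 mg and is absent at the other four. The figures show consequence and not likelihood: the documents give no rate for the event, and one of the four Table 15 scenarios checked does not reproduce. The point concerns the rule as printed, and is worth correcting before this DLT definition is used again.

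**What to change.** In the neutropenia bullet, replace the clause that requires absence of myelodysplasia or leukemic transformation with: *unless determined by the SRC to be due solely to MDS-related marrow failure, progression of MDS or transformation to acute leukemia*. This brings it into line with the platelet bullet and the Note. Extend the Note's SRC review to all new Grade 4 neutropenia not recovering within 7 days, whatever the patient's history.

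The cost is one phrase and a wider scope for one Note sentence. No new data or procedures are needed, because the SRC already reviews each cohort. The downside is slightly more SRC review and possibly more events counted as DLTs.
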